Participants will consist of 400 pairs of children and their caregivers (total N = 800). This replicates cell sizes in the pilot data and allows close comparability, with 100 children and 100 adults in each of four cells. The caregivers consist of the second generation participants (their parents are the first generation) who originally comprised the birth cohort. Their adolescent children are the third generation. All caregivers have previously participated in the Mauritius Child Health Project (Raine et al., 2010). Adolescents will be aged between 11 and 18 years old, willing to participate in an RCT, and residing in the community. Exclusion criteria consist of: (1) allergy to fish or fish products, (2) use of fish oil supplementation in the past six months, (3) intellectual disability, (4) participation in the prior RCT. There are currently 1,126 children aged 11-18 years actively participating in the Mauritius Child Health Project (51.2% female; 73.2% Indian, 24.5% Creole, 2.3% other), 124 of whom took part in the prior RCT and will be excluded. Written informed consent will be obtained from the parents with assent obtained from adolescents. The study will take place in interview rooms at the project headquarters in Quatre Bornes.

Attrition is an issue in all RCTs. In our pilot data however, attrition was only 8%, even after one year, and is likely attributable both to the long-standing intergenerational relationships between our research team in Mauritius and the participants. Attrition may nevertheless be slightly more with the longer follow-up. We have three strategies to deal with attrition. First, analyses will be intention-to-treat, including all participants regardless of drop-outs. Second, we will enhance participation using staggered incentives for completion. Third, we will code for missingness and assess whether it moderates treatment outcome.

Randomization

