The parent (CBCL) and youth (YSR) reports also include School Competence scales, while the teacher (TRF) form includes Academic Performance and Adaptive Functioning (Achenbach et al., 2015). These will extend the scope on mechanistic processes beyond neurocognitive functioning.

As in the pilot study, parental belief in treatment allocation to the omega-3 group (yes, no) will be measured at the end of treatment to assess influence on behavioral change. Demographics will again be collected on entry into the study, together with an adverse events questionnaire at the end of treatment.

Adherence to protocol and blood assays.

Adherence to the treatment regimen is a frequent problem in RCTs. As before, this will be assessed by assays of omega-3 from finger-prick blood taken from both caregiver and adolescent at all four time-points, with microwave irradiation assays conducted by team member [name] an NIAAA. For full methodological details see Lin, Loewke, Hyun, Leazer, & Hibbeln (2012). In response to C2, blood will additionally be assessed mid-way through supplementation (3 months). To help further enhance adherence, participants will be called every two weeks to remind them to use supplements, and to assess frequency of drink consumption by caregiver and adolescent in that time period (number of drinks / two weeks). To further facilitate compliance, participants will be given a bonus payment if their % blood omega-3 levels have risen higher than the bottom quartile of the population.

Statistical Methods

Overview. An intention-to-treat (ITT) design using all randomly assigned participants will be employed for all data analyses. All data will be blindly double-entered and checked for consistency.

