For the adolescent, Hypothesis 1a will be addressed using a child group by time interaction term (time trends for omega-3 and placebo group need not be parallel), or a child group main effect if the interaction term is non-significant (parallel time trends). Similar models will address the corresponding Hypothesis 1b for the caregiver responses. For both the adolescent and caregiver responses, Hypothesis 2a will be tested by an adolescent group by caregiver group by time interaction, or by an adolescent by caregiver interaction if the four adolescent by caregiver group trends are parallel.

Aim 3 (Secondary Outcome). Working hypothesis 3a (change in neurocognitive and academic factors) will be tested using the same mixed effects models as outlined above in aims 1 and 2. Working hypothesis 3b (mediation), whether improvement in neurocognitive variables (e.g. impulse control) or academic WRAT scores partly account for the treatment effect on child behavior will be assessed using mediation analyses. Based on the prior study (Raine et al, 2015), effects of supplementation should emerge by the 12-month time point. Analyses will test whether changes in risk factors between baseline and the 6 month point mediate the 12-

month treatment effect. These analyses will be conducted using the PROCESS SPSS macro (Hayes, 2012), which will also be used to assess moderated mediation (e.g. neurocognitive measures mediate outcomes more strongly in younger adolescents). To test significance of the indirect effects (i.e. mediation), bias-corrected confidence intervals for the indirect effects will be generated using 10,000 bootstrap samples. To assess extent of mediation, the reduction in variance explained in treatment outcome by the intervention after controlling for improved parental behavior (the mediator) will be calculated in a two-step regression. Equivalent analyses will be performed for the other neurocognitive variables.

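### The plan promises that every randomized participant enters every analysis, but the hypothesis 3b mediation regressions, as written, can use only children with complete baseline, 6-month and 12-month data

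*Combined protocol and SAP*

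**What the plan says.** The promise about who is analysed is made twice in the combined protocol and SAP, without exception for secondary or mediation analyses.

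- Statistical Methods, Overview: "An intention-to-treat (ITT) design using all randomly assigned participants will be employed for all data analyses".
- Participants, Potential Attrition, and Strategies to Deal with Attrition, as the first of three strategies against attrition: "analyses will be intention-to-treat, including all participants regardless of drop-outs".

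The second strategy is staggered payment for completion. The third is the only other analytic provision for missing data: "Third, we will code for missingness and assess whether it moderates treatment outcome".

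Aims 1 and 2 use linear mixed effects models, and hypothesis 3a uses the same models. Hypothesis 3b, under Aim 3 (Secondary Outcome), changes method. The mediator is the change in a risk factor from baseline to 6 months, and the effect to be explained is the one at 12 months. Of the software the plan says: "These analyses will be conducted using the PROCESS SPSS macro". The same macro is to be used for moderated mediation. Indirect effects get bias-corrected intervals from 10,000 bootstrap samples, and the extent of mediation comes from a two-step regression. No imputation or likelihood method for missing values is given for 3b.

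**The concern.** A linear mixed model can keep a child who misses some visits, because each observed visit contributes. A regression with one row per child cannot. If the change score or the 12-month outcome is absent, that row cannot be used. The method named for 3b therefore does not deliver the property that the plan states for all its analyses.

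Two things are at stake. The smaller is precision. The larger is selection: if drop-out depends on arm and on prognosis, the two quantities in 3b that begin with treatment (the treatment-to-mediator path and the 12-month treatment effect) are no longer comparisons of the groups as randomized.

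There is also a practical consequence. The plan lists six CANTAB tasks and several WRAT-4 scores as candidate mediators. Each may have its own missing values, so each mediation result could rest on a different subset of children, with no rule for this stated.

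**Working it through.** **Inputs from the document**

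- Allocation: "with 100 children and 100 adults in each of four cells".
- Attrition: "In our pilot data however, attrition was only 8%, even after one year". For this trial the plan expects possibly slightly more because follow-up is longer, and gives no figure.
- Visits that 3b needs: baseline and 6 months for the mediator, 12 months for the outcome.

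**The plan's own sample size.** 4 cells × 100 = 400 pairs, and 400 × 2 = 800 individuals. This agrees with the stated 400 pairs and total of 800. The child is the unit in 3b, so the promised analysis set is 400.

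**What each step of 3b needs**

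1. Mediator on treatment: baseline and 6-month mediator values.
2. Outcome on treatment and mediator: both mediator values and the 12-month outcome.
3. Indirect effect, bootstrapped over one common set of children: all three values.
4. Two-step regression: the 12-month outcome in both steps, and the mediator in the second.

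This follows from the form of the regressions. It does not rely on how the macro treats missing values, which the document does not describe.

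**Size at the documented rate.** Take 8% as the proportion lost by 12 months, with nothing else missing and losses spread evenly over the cells.

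- Left out: 400 × 0.08 = 32.
- Analysed: 400 − 32 = 368, or 368 / 4 = 92 per cell.
- Standard error relative to 400 complete children: √(400 / 368) = 1.043, about 4% larger.

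**Sensitivity to assumed rates.** None of these rates comes from the document.

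| Assumed loss | Left out | Analysed | Standard error ratio |
|---|---|---|---|
| 5% | 20 | 380 | 1.026 |
| 10% | 40 | 360 | 1.054 |
| 15% | 60 | 340 | 1.085 |
| 20% | 80 | 320 | 1.118 |

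If 6-month and 12-month data were each missing independently in 8%, the analysed number would be 400 × 0.92² = 338.6, about 339, with a ratio of 1 / 0.92 = 1.087.

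The ratios compare with 400 fully observed children. Imputation or full-information likelihood would recover only part of that loss.

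**Does another provision close the gap?** Coding missingness and testing it as a moderator may show that missingness matters. It does not supply a change score or a 12-month outcome, so it returns no excluded child to the 3b regressions.

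**The case against.** The strongest reply is that the plan is silent, not contradictory. It never calls 3b a complete-case analysis, and it could be read as leaving the missing-data method to be chosen so that the intention-to-treat statement is met. It also plans completion incentives and a check on missingness, pilot attrition was low, and 3b is a secondary working hypothesis. Part of this stands: the plan does not rule out imputation, so the point holds only for the analysis as written. Silence does not answer it, however. The reader is told that everyone is included, and the one method named for 3b cannot include everyone without a further step.

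Several stronger readings are tempting, and the document does not support them.

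- *The indirect effect loses a protection by randomization that the plan claims for it.* The plan makes no such claim. Its statement that randomization removes selection bias is used under Aims 1 and 2 to justify leaving baseline covariates out of the primary analyses. The mediator-to-outcome path would not be randomized even with complete data.
- *A mediated effect in completers will be set against a treatment effect estimated in everyone.* The plan does not make that comparison. The two-step regression compares variance explained before and after adding the mediator, and both steps can use the same children.
- *The longer follow-up makes the loss in 3b worse.* The 18-month visit does not enter 3b, and the pilot's 8% already covers one year, which is the relevant horizon. Missed 6-month tests could raise the loss, but their rate is unknown.
- *Bias has been shown.* It has not. The document gives no drop-out by arm, so neither direction nor size can be stated.

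**Conclusion.** The point holds in a limited form. The statement that all randomized participants enter all analyses is not met by the 3b regressions, including moderated mediation, as they are written. The only size that rests on the document's own attrition figure is about 32 of 400 children left out and standard errors about 4% larger. It assumes that pilot attrition carries over and that there is no other missing data. That loss of precision is modest. The more important risk is possible bias from selective drop-out in the treatment-to-mediator path and in the 12-month treatment effect within 3b. A reader should not extend this to the primary analyses or to hypothesis 3a, whose mixed models can use partial follow-up. This is a minor point about one secondary hypothesis, worth correcting because the correction is cheap.

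**What to change.** Preferred: state a missing-data method for 3b that uses visits already planned. There are two options.

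- Fit the mediation and moderated-mediation models by full-information maximum likelihood.
- Multiply impute the mediators and the 12-month outcome within each of the four randomized cells, using baseline and all other visits. Include a stated rule for combining the imputations with the 10,000-sample bootstrap intervals.

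Under either option, state the missing-at-random assumption and report the complete-case results as a sensitivity analysis.

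If neither is adopted, limit the intention-to-treat sentence in the Overview, and its counterpart in the attrition section, to the analyses that meet it. Label 3b as complete-case and report the number of children analysed per cell for each mediator.

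Cost: the first route takes some extra analysis work and relies on missing-at-random, which the data cannot confirm. The second takes about a sentence, but leaves the possible selection in place.

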Aims 1 and 2 (Primary Outcome). These hypotheses will be addressed using adolescent and caregiver externalizing responses gathered at baseline and at 6, 12, and 18 month follow-ups. Responses for the adolescent will be analyzed separately from responses for the caregiver. For each separate set of responses, linear mixed effects models (Molenberghs & Verbeke, 2005) will be used to describe both the pattern of response and the within-subject covariance structure across time points. Primary analyses will not include baseline covariates, as the randomization will balance the treatment groups and eliminate selection bias. To enhance power by controlling for variability in response (Kahan et al., 2014), a small set of baseline covariates (e.g. gender, age, ethnicity) will be included in supplementary analyses.

The response may be transformed (e.g. log transformation) to reduce levels of skewness in the response to acceptable levels, as assessed by examination of residuals. Models will include binary indicators for adolescent group (omega-3 vs placebo), caregiver group (omega-3 vs placebo), and time (four level factor for times 0, 6, 12, and 18), and group by time interaction terms, as fixed effects. Time is modeled as a discrete factor to accommodate the patterns observed in our prior study (see Figure under Preliminary Data) where the omega-3 adolescent groups are similar at baseline and 6 months, and separate at 12 months. Covariance structure models (e.g. random effects, autocorrelated residuals) will be compared using information criteria in models containing all main effects and interactions of interest. Once the covariance structure has been chosen, the fixed effects will be assessed for significance using likelihood ratio tests.

Parameter estimates, standard errors, and 95% confidence intervals will be reported. In the case of a multiple degree of freedom test (e.g. group by time interaction, with 3 df), single-df contrasts will be estimated and reported, to explain the nature of the interaction.

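### The planned group-by-time test is valid, but it estimates a month-0 group difference that randomisation makes zero; a common baseline mean would sharpen contrasts against month 0

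*Combined protocol and SAP*

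**What the plan says.** Under Statistical Methods, Aims 1 and 2 (Primary Outcome), the responses analysed are "adolescent and caregiver externalizing responses gathered at baseline and at 6, 12, and 18 month follow-ups", so the month-0 score is an outcome and not a covariate. The fixed effects are the child and caregiver group indicators, "and time (four level factor for times 0, 6, 12, and 18), and group by time interaction terms, as fixed effects".

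The same section says: "Primary analyses will not include baseline covariates, as the randomization will balance the treatment groups and eliminate selection bias". For added power, "a small set of baseline covariates (e.g. gender, age, ethnicity) will be included in supplementary analyses"; the baseline externalizing score is not among the examples.

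The test is then set: "Hypothesis 1a will be addressed using a child group by time interaction term", "or a child group main effect if the interaction term is non-significant (parallel time trends". Hypothesis 1b is handled in the same way. Hypothesis 2a uses the three-way interaction with time, or the child-by-caregiver interaction if the four trends are parallel. Hypothesis 3a uses the same models (Aim 3). After a multiple-df test, "single-df contrasts will be estimated and reported, to explain the nature of the interaction".

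Nothing in the documents constrains the four cells to a common mean at month 0.

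**The concern.** A four-level time factor with a 3-df group-by-time term leaves one free group difference at month 0 and three departures from it. Each departure is the arm difference at a follow-up visit minus the arm difference at month 0, that is, a difference in mean change.

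Design Overview calls month 0 baseline and month 6 the end of supplementation, and treatment lasts six months. Month 0 therefore precedes treatment, and with random allocation the true arm difference there is zero. The plan relies on this argument itself when it leaves baseline covariates out of the primary analysis. Estimating that difference anyway adds its sampling error to every contrast against month 0.

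Hypotheses 1a, 1b, 2a and 3a all use this model. Precision is tightest for 2a, the question that the factorial design adds. The sample size was set by matching the pilot's cell sizes, with no stated power calculation, so the documents show no margin against which to judge the loss.

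**Working it through.** **Inputs from the documents.** The design is "with 100 children and 100 adults in each of four cells" (Participants section): 4 × 100 = 400 pairs and 2 × 400 = 800 people, which agree. Each factorial margin is 200 v 200. There is no power figure to reproduce.

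**Assumptions.** Equal SD at all visits (results in SD units); equal correlation ρ between any two visits, not given and varied below; two-sided 5% level, not stated but in keeping with the planned 95% intervals; complete data; effects of 0.25 or 0.20 SD for illustration.

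**Step 1: one contrast against month 0.** Let d_t be the difference in arm means at month t, with n = 200 per arm. Then var(d_t) = 2/n and cov(d_t, d_0) = 2ρ/n.

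- Planned model: the estimate is d_t − d_0, with variance (2/n) × 2(1−ρ).
- Common month-0 mean: the estimate is d_t − ρd_0, with variance (2/n) × (1−ρ²).
- Ratio: (1−ρ²) / [2(1−ρ)] = (1+ρ)/2, so the variance falls by (1−ρ)/2.

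Power for 0.25 SD is Φ(0.25/SE − 1.96).

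| ρ | Variance cut | SE planned | SE common mean | Power planned | Power common mean |
|---|---|---|---|---|---|
| 0.3 | 35% | 0.118 | 0.095 | 56% | 75% |
| 0.5 | 25% | 0.100 | 0.087 | 71% | 82% |
| 0.6 | 20% | 0.089 | 0.080 | 80% | 88% |
| 0.7 | 15% | 0.077 | 0.071 | 90% | 94% |

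The SE is multiplied by √((1+ρ)/2): 0.866 at ρ = 0.5 and 0.922 at ρ = 0.7, a fall of 13% to 8%. For these contrasts the gain matches 400/0.75 = 533 pairs at ρ = 0.5, or 400/0.85 = 471 at ρ = 0.7.

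**Step 2: the 3-df test.** For effects δ at months 6, 12 and 18 the noncentrality is n/[2(1−ρ)] × [Σδ² − k(Σδ)²], with k = 1/4 as planned and k = ρ/(1+3ρ) with a common mean. Take 0.20 SD at months 12 and 18 only, so Σδ² = 0.08 and (Σδ)² = 0.16.

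- ρ = 0.5: planned 200 × (0.08 − 0.04) = 8.0; common mean 200 × (0.08 − 0.032) = 9.6. Power 65% to 74%.
- ρ = 0.7: planned 333.3 × 0.04 = 13.3; common mean 333.3 × (0.08 − 0.0361) = 14.6. Power 88% to 91%.

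**Step 3: Hypothesis 2a.** The difference of differences over four cells of 100 has variance (4/100) × 2(1−ρ) as planned and (4/100) × (1−ρ²) with a common mean. At ρ = 0.5 the SE falls from 0.20 to 0.17 SD. The planned SE is twice that of a main-effect contrast; the relative saving is the same.

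**Step 4: contrasts that do not gain.** The month-18 minus month-12 arm difference has variance (2/n) × 2(1−ρ) under both models when correlations are equal.

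**Step 5: the fallback.** The main effect averages all four visits, including month 0. Under equal correlation, a constant 0.30 SD effect at months 6, 12 and 18 is estimated as 0.30 × 3/4 = 0.225 SD, and a 0.30 SD effect at months 12 and 18 only as 0.30 × 2/4 = 0.15 SD.

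**Step 6: sensitivity.** With assumed dropout of 4, 8 and 12% at months 6, 12 and 18, the variance cuts are 24.2, 23.6 and 22.9% at ρ = 0.5, and 14.5, 14.1 and 13.6% at ρ = 0.7. If correlation decays as AR(1) with adjacent-visit values of 0.5 to 0.7, the cut is 37.5 to 25.5% at month 12 and 43.8 to 32.8% at month 18.

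**The case against.** The strongest reply is that group, time and group-by-time is a standard model, unbiased under randomisation, and that the authors considered precision and placed covariate adjustment in supplementary analyses. The first part stands: this is lost efficiency, not an error. The second does not recover the loss, since those analyses are not primary and the baseline score is not named for them.

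A reader might infer that every effect in the plan is a change score. The documents do not support that. The fallback main effect and child-by-caregiver interaction average over visits, and the plan does not say that every single-df contrast is taken against month 0.

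A reader might also take the gain as large and settled. It rests on a correlation that the documents do not give, and at 0.7 it is modest.

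The most striking figure would come from assuming 0.20 SD at all three follow-ups with ρ = 0.5, where the 3-df test goes from 52% to 74%. That 52% is not the power of the plan as written. With the fallback, the two-step procedure rejects about 75% of the time in that case, though at about 10% type I error if each step uses 0.05. The constant pattern is also not the one the plan expects, which is similar groups at month 6 and separation at month 12. The 65% and 88% in Step 2 likewise describe the interaction step alone.

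**Conclusion.** The point holds as an efficiency recommendation. Contrasts against month 0 carry avoidable baseline sampling error, because a difference known to be zero by design is estimated. Under equal correlation the avoidable share of their variance is 15 to 25% at ρ of 0.5 to 0.7, and 35% at 0.3. The direction is not in doubt: the ratio (1+ρ)/2 is below 1 for any ρ below 1. The size depends on the unstated correlation between month 0 and the visit concerned, and the power figures also depend on assumed effects and complete data.

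A reader might infer that the planned test is biased or would mislead. It would not. The fallback has a separate weakness, dilution by a visit at which no effect can exist, and a common month-0 mean tested only over follow-up visits removes that too.

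**What to change.** Keep all four visits as outcomes and give all four cells one common mean at month 0. The fixed effects become time (four levels), child group at months 6, 12 and 18, caregiver group at months 6, 12 and 18, and the child-by-caregiver terms at those three months for Hypothesis 2a. Test 1a, 1b, 2a and 3a each by the 3-df likelihood-ratio test of the relevant group terms at months 6, 12 and 18, and report the month-specific estimates with intervals.

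State explicitly that this single test replaces the fallback to a group main effect or a child-by-caregiver interaction. That is a real change to the testing rule and not only to the parameterisation, so it should be fixed before unblinding.

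The cost is about one paragraph of SAP wording, with no new data or participants. The only design condition is that month 0 is measured before the first drink, which the plan implies by calling it baseline.

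### The primary model's covariance is left to an unnamed information criterion over an open candidate list; if a structured form is picked, the visit contrasts can carry wrong standard errors, and pre-specifying an unstructured matrix avoids this at almost no cost

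*Combined protocol and SAP*

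**What the plan says.** The rule is in Statistical Methods, Aims 1 and 2 (Primary Outcome). Time enters as a factor with four levels (0, 6, 12 and 18 months). On the covariance the plan says: "Covariance structure models (e.g. random effects, autocorrelated residuals) will be compared using information criteria", with the full set of fixed effects in the model. It continues: "Once the covariance structure has been chosen, the fixed effects will be assessed for significance using likelihood ratio tests". Estimates, standard errors and 95% intervals are reported from that model, and after a multi-df test such as the 3-df group-by-time interaction, "single-df contrasts will be estimated and reported, to explain the nature of the interaction".

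The same section states: "Responses for the adolescent will be analyzed separately from responses for the caregiver". The participants section gives 400 pairs, "with 100 children and 100 adults in each of four cells", so each model has up to 400 subjects. Aim 3 reuses these models for the neurocognitive and academic outcomes, and the moderator analyses extend them.

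The plan does not say whether AIC or BIC is used, which structures form the closed candidate set, or whether robust standard errors or an unstructured sensitivity analysis will be run. An unstructured matrix is neither named nor excluded.

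**The concern.** Both named examples impose a pattern on the variances and correlations. Scores may change in spread after baseline, or correlate less with baseline than with each other. The best-fitting structured form can then still misstate the variance of a particular visit difference, and its model-based standard error is used as if it were right.

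The visit contrasts carry the timing. The plan treats time as discrete because the pilot groups separated at 12 months rather than at 6, and Aim 3 expects effects by 12 months. The 3-df test cannot show when an effect appears or whether it lasts to 18 months; only the contrasts can. An error in their standard errors therefore falls on the statements most likely to be read from the trial.

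**Working it through.** **Figures from the plan.** 4 cells × 100 = 400 pairs, × 2 = 800 persons, as stated. Group-by-time df = (2 − 1)(4 − 1) = 3, as stated. An unstructured matrix for four visits has 4 × 5 / 2 = 10 parameters. At the pilot's 8% attrition, 400 × 0.92 = 368 subjects remain per model.

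**Assumptions.** Alpha is not stated; two-sided 5% is assumed, in line with the 95% intervals. No variance or correlation is given, so every matrix below is assumed. The structured candidates tried were random intercept, AR(1), random intercept + AR(1), and random intercept + slope.

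**Formula.** With complete data and a separate mean for each group and visit, a visit contrast *c* is the same difference of cell means under every covariance. Only its standard error changes. If T is the true matrix and S the fitted one, the standard-error ratio is r = √(c′Sc / c′Tc), and the actual size of a nominal 5% test is 2Φ(−1.96 r).

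**A milder pattern, by hand.** Assume variance 1 at every visit, correlation 0.55 with baseline and 0.65 among follow-ups.
- The best random-intercept fit has the mean correlation, (3 × 0.55 + 3 × 0.65) / 6 = 0.60, so c′Sc = 2(1 − 0.60) = 0.80 for any two visits.
- 6 or 12 months v baseline: c′Tc = 2(1 − 0.55) = 0.90; r = √(0.80/0.90) = 0.943; size 6.5%.
- 18 v 12 months: c′Tc = 2(1 − 0.65) = 0.70; r = √(0.80/0.70) = 1.069; size 3.6%.
- Deviance gained by the unstructured matrix: det S = (1 + 3 × 0.6)(0.4)³ = 0.1792. det T = (2.3)(0.35)² × (1 − 0.55² × 3/2.3) = 0.1706. 400 × ln(0.1792/0.1706) ≈ 19.7.
- BIC charges (10 − 2) × ln 400 = 47.9 for it, so BIC keeps the random intercept. AIC charges 16, so the choice is close. The unnamed criterion therefore matters.

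**Simulated size with AIC among structured forms only**, 1,000 trials of 400 per matrix (Monte Carlo error about ±1.4 points around 5%), against unstructured fixed in advance. Entries are % at 6 / 12 / 18 months v baseline.

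| Assumed truth | Structured, AIC | Unstructured fixed |
|---|---|---|
| Correlation 0.6, constant variance | 5.5 / 5.4 / 6.1 | 5.6 / 5.2 / 6.5 |
| Correlation 0.7/0.6/0.5 by lag, constant variance | 5.4 / 4.5 / 4.9 | 5.2 / 4.8 / 4.8 |
| Correlation 0.6, variance 1, 0.8, 0.7, 0.6 | 6.9 / 5.5 / 5.6 | 4.9 / 4.7 / 5.4 |
| Correlation 0.7/0.6/0.5, variance 1, 1.1, 1.3, 1.5 | 3.5 / 4.8 / 5.6 | 5.2 / 5.2 / 5.7 |
| Baseline 0.5, follow-up 0.7, constant variance | 10.4 / 7.4 / 6.5 | 5.9 / 4.8 / 5.9 |
| Same, variance 1, 0.8, 0.7, 0.6 | 10.9 / 8.6 / 6.4 | 5.0 / 5.1 / 5.5 |

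In the last row the large-sample ratios for random intercept + slope are 0.81 / 0.87 / 0.96, which the formula turns into 11.2% / 8.8% / 6.0%. For 18 v 12 months, large-sample sizes under the last two patterns were 2.9% and 1.7% (the second with SDs 1, 0.9, 0.85, 0.8).

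**Adding unstructured as a candidate.** In the last two rows AIC chose it in 100% of trials and BIC in 97–100%, and size returned to 4.8–6.0%. In the third and fourth rows AIC chose it in 87–89% but BIC in only 5–6%, leaving 6-month size under BIC at 6.8% and 3.5%.

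**Tests that decide the hypotheses.** The large-sample size of the 3-df test was at most 6.1% under any structure tried. Its simulated size was 4.8–6.5% with AIC among structured forms and 4.4–6.7% with unstructured fixed, so the two do not differ beyond noise. The group main-effect test stayed at 5% in the two worst patterns.

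**The case against.** The strongest reply is that the examples follow an "e.g.". A reader might infer that the plan confines itself to structured forms; the text does not say so. With four visits and time as a factor, an unstructured matrix is an ordinary candidate, and the planned rule would then select it in the patterns where the error is large. That stands, and it limits the finding. What remains is that nothing commits the analyst to include it, and that under BIC it is passed over in the milder patterns.

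A reader might also infer that the primary test has an inflated error rate. The calculations do not support this: Hypothesis 1a rests on the interaction or main-effect test, both near nominal. The contrasts have an explanatory role, and if they are read only after a significant interaction, the chance under the global null of both occurring cannot exceed the 3-df rate. The percentages above are unconditional. The reported standard errors and 95% intervals are nonetheless wrong by the same factor however the contrasts are used.

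It can further be said that selection on the trial's data cannot be used to favour an estimate. With complete data that is right, because the contrast estimates are identical under every structure. With dropout the choice can also move estimates; this was not simulated.

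Finally, the matrices are assumed, and four of the six gave only 3.5–6.9% even with structured forms alone. The planned residual checks and possible log transformation might also reduce variance changes tied to the mean. Both points are fair, and they are why the size is given as a range.

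**Conclusion.** The concern holds in a limited form. The plan leaves the covariance of its primary models to a data-driven choice with neither the criterion nor the candidate set fixed, and it has no robust standard error as a safeguard. If a structured form is chosen and does not match the truth, the visit contrasts can be too liberal against baseline (up to about 11% at 6 months and 9% at 12 months) and too conservative between follow-ups (down to about 2% for 18 v 12 months). The upper figures require that only structured forms are compared; where BIC passes over an available unstructured matrix, the milder pattern gives about 7% at 6 and 12 months. All figures assume complete data, two-sided 5% tests and covariance matrices that the documents do not supply. The documents do not show that the planned analysis will have wrong standard errors, only that nothing in the plan prevents it.

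**What to change.** In Statistical Methods, Aims 1 and 2, replace selection by information criteria with a pre-specified unstructured within-subject covariance for both the adolescent and the caregiver primary models. State a fallback order to be used only if that fit does not converge, for example heterogeneous structured forms with robust standard errors. Without such an order the fallback would itself be a choice made on the data.

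The cost is wording only. The structured forms tried have 2 to 4 parameters, so the change adds 6 to 8 covariance parameters, estimated from 400 subjects (about 368 at the pilot's attrition). Across the six assumed matrices, the change-from-baseline contrasts then ran at 4.7–6.5%, and the worst 6-month figure fell from 10.9% to 5.0%. No extra data or visits are needed.
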